### 7.3.2 Laboratory Data

Laboratory tests will be reported separately for hematology and blood chemistry.

For the purposes of presentation in both tables and listings, the following laboratory test results will be converted to the International System of Units (SI) before presentation: sodium, potassium, chloride, bicarbonate (or CO2), albumin, total protein, creatinine, uric acid, calcium, phosphorus, magnesium, glucose, total and direct bilirubin, and alkaline phosphatase, red blood cell (RBC) count, hemoglobin, hematocrit, platelets, white blood cell count with 5-part differential performed manually or by flow cytometry (lymphocytes, neutrophils, monocytes, basophils, and eosinophils), etc.

Lab tests performed after the start of the first dose of study treatment, up to 30 days from the last dose, will be considered treatment-emergent. Only treatment-emergent lab tests will be included in the analyses in this section.

If a laboratory test value is reported using a non-numeric qualifier (e.g., less than [ $<$ ] a certain value, or greater than [ $>$ ] a certain value), the given numeric value will be used in the summary statistics, ignoring the non-numeric qualifier.

For laboratory tests with NCI-CTCAE grades, a shift table from baseline grade to the maximum post-baseline grade will be provided. Laboratory tests with bi-directional grades (e.g., Hyperglycemia and Hypoglycemia) will be presented separately for each direction within the shift table.

Listings will be provided for all laboratory test results and for laboratory test results grade 3 and higher. A listing of subjects with ALT or AST  $>3xULN$  with simultaneous total bilirubin  $>2xULN$  will be presented, where ULN stands for upper limit of normal. The elevations of ALT/AST and total bilirubin must occur within 2 days of each other.

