- n. The Early Treatment Termination (ETT) Visit should occur for any subject who discontinues ofatumumab treatment prior to Cycle 7 Day 1. ETT assessments need not be performed for those assessments performed within the previous 2 weeks (previous 30 days for Disease Response Assessments [see [Table 5](#)] and the QoL assessment).
- o. The clinical visit schedule should be maintained until Cycle 9 for subjects who discontinue study treatment prior to Cycle 9 for reasons other than PD. The clinical assessment period then begins at Cycle 9, with visits occurring every other month until disease progression, subject withdrawal, or initiation of additional anticancer therapy; no additional study drug (ofatumumab) will be administered.

Table 5: Disease Response & Follow-up Assessments for All Subjects

Assessments ^d	Screening (baseline)	Cycle 3 Day 1	Cycles 5, 7, 11, 15, & 19 Day 1	Early Termination from Study Treatment (ETT) ^a ≤7 days of last dose	Disease Follow-up ^b Every 6 months (±4 weeks)	Survival Follow-up ^c Every 6 months (± 4 weeks)
CT scans of chest, abdomen and pelvis ^e	X	X	X	X	X	
Bone marrow biopsy and/or bone marrow aspiration ^f	X	X	X	X	X	
Complete blood count (CBC) and differential count ^g	X	X	X	X	X ⁱ	
Blood sample for assessment for minimum residual disease (MRD) ^h		X	X	X	X	
Focused physical examination ^g , disease related constitutional symptoms assessment, and ECOG performance status	X	X	X	X	X	
Survival						X

- a. ETT Disease Response Assessment is not necessary if a Disease Response Assessment was performed within the previous 30 days. In the absence of disease progression or initiation of subsequent anticancer therapy, all subjects with ETT prior to Cycle 19 Day 1 will maintain the disease response assessment schedule (Cycles 5, 7, 11, 15, & 19)
- b. All subjects with no disease progression by Cycle 19 Day 1 will continue Disease Response Assessments (Section 6.5.3.1) every 6 months until disease progression, subject withdrawal, or initiation of additional anticancer therapy. The first disease follow-up assessment after Cycle 19 Day 1 should occur approximately 6 months after last disease assessment.
- c. All subjects will have Survival Follow-up for up to 6 years after randomization or until death. This assessment can be conducted by telephone interview. Information on initiation of other anticancer therapy (including start date, therapy type, and response on treatment) will also be collected.

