4.1 SCHEDULE OF ADMINISTRATION

Subjects who meet all the eligibility criteria at Screening will return to the clinic on Day 1 to receive their first dose of study drug (either duvelisib or ofatumumab). The first treatment cycle for each treatment arm will be 3 weeks (21±2 days). Subsequent treatment cycles will be 4 weeks (28±4 days).

Arm 1 (Duvelisib): Subjects randomized to duvelisib will receive their first dose of study drug in clinic on Day 1, initiating Cycle 1 of treatment. These subjects will return for a second clinical visit on Day 8±2. Cycle 1 will be 21 days, with all subsequent cycles 28 days in length. Cycle 2 will have clinic visits on Day 1 and on Day 15±2. Each subsequent cycle (Cycle 3-7) and then every odd cycle (Cycle 9 to 19) will have only one clinic visit on Day 1. Subjects will receive duvelisib continuously for 18 cycles or until disease progression or unacceptable toxicity, whichever comes first. After completing approximately 18 cycles of treatment with duvelisib, subjects who, in the judgment of the investigator, may derive benefit from continued treatment may receive additional cycles of duvelisib until disease progression or unacceptable toxicity. However, to receive additional cycles of duvelisib beyond 18 cycles, subjects must have CLL/SLL requiring treatment by Cycle 19 Day 1 (Reference 4.2.1.2). Subjects who receive duvelisib beyond 18 cycles (Cycle 19 Day 1) will maintain clinical visits every odd cycle (Cycle 21, 23, etc) until disease progression, subject withdrawal, or initiation of additional anticancer treatment. After Cycle 18, disease response assessments will continue every 6 cycles for those subjects who have not had disease progression, withdrawn consent, or initiated additional anticancer treatment.

Arm 2 (Ofatumumab): Subjects randomized to ofatumumab will receive IV treatment according to the approved prescribing information.^{10, 11} Subjects will receive 8 weekly IV infusions, starting with an initial dose of ofatumumab of 300 mg followed by seven weekly doses of 2000 mg. Thereafter, subjects will receive 2000 mg ofatumumab once every cycle for four cycles or until disease progression or unacceptable toxicity, whichever comes first.

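### The laboratory shift table takes each subject's worst grade over windows of unequal length (8 scheduled draws for ofatumumab completers, 14 by Cycle 19 on duvelisib), and no common-window table is planned for comparing the arms

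*SAP*

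**What the plan says.** SAP V4.0 section 7.3.2 defines the laboratory window by a single rule for both arms: "Lab tests performed after the start of the first dose of study treatment, up to 30 days from the last dose, will be considered treatment-emergent". It adds that "Only treatment-emergent lab tests will be included in the analyses in this section". Within that window the only tabulated summary is the shift table, described as "a shift table from baseline grade to the maximum post-baseline grade will be provided"; the remaining laboratory outputs are listings. SAP 6.7 lets unscheduled draws enter worst post-baseline values.

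Protocol 4.1 sets the duvelisib visits. In Cycle 1, "These subjects will return for a second clinical visit on Day 8±2". Next, "Cycle 2 will have clinic visits on Day 1 and on Day 15±2". Cycles 3 to 7 have a Day 1 visit each, "then every odd cycle (Cycle 9 to 19) will have only one clinic visit on Day 1". Table 2 marks chemistry and hematology at all of these visits.

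Table 4 marks chemistry and hematology on ofatumumab at the same days through Cycle 7, and again at Cycles 9 to 19. The 30-day safety visit has no scheduled laboratory test and may be a telephone contact (Protocol 6.5.1.2). Footnote n limits the termination visit to early stoppers: "The Early Treatment Termination (ETT) Visit should occur for any subject who discontinues ofatumumab treatment prior to Cycle 7 Day 1". Footnote o covers the period after treatment: "The clinical assessment period then begins at Cycle 9, with visits occurring every other month until disease progression".

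SAP 7.3.1 plans adverse event tables restricted to onset within 24 weeks of first dose, both overall and for Grade 3 or higher. Section 7.3.2 has no laboratory equivalent.

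**The concern.** A per-subject maximum can only stay the same or rise as draws are added. If one arm is observed over more draws and more time, its worst-grade percentages will tend to be higher even when the risk at each draw is the same. Here the difference in window is built into the design: ofatumumab is a fixed course ending at Cycle 7, whereas duvelisib runs to 18 cycles and may continue. The last-dose-plus-30-day rule then removes ofatumumab draws that the protocol collects.

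Changes in safety laboratory values are a named secondary endpoint (Protocol 3.2, SAP 5.2). The shift table is the natural place to read neutropenia or transaminase grades side by side. Without a common-window table, a reader cannot separate a difference between drugs from a difference in length of observation.

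**Working it through.** **Check on the reading of the tables.** Take Cycle 1 as 21 days and later cycles as 28 days, so that for cycle k of 2 or more, Day 1 falls on study day 22 + 28(k − 2). The infusion columns of Table 4 give 3 infusions in Cycle 1, 4 in Cycle 2 and 5 in Cycles 3 to 7: 3 + 4 + 5 = 12. This matches the protocol's stated 12 doses within 7 cycles. The last is on day 22 + 28 × 5 = 162.

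**Scheduled post-baseline draws** (Cycle 1 Day 1 is predose, hence baseline):
- Both arms through Cycle 7: C1D8, C2D1, C2D15 and C3 to C7 D1, on days 8, 22, 36, 50, 78, 106, 134 and 162. That is 8 draws.
- Duvelisib while dosing continues: also C9, 11, 13, 15, 17 and 19, on days 218 to 498. That is 8 + 6 = 14.
- Ofatumumab after 12 infusions: the window closes on day 162 + 30 = 192. C9D1 is on day 218, which is 56 days after the last infusion, and at least 48 with both visits at the edge of their ±4-day windows. All six draws from C9 to C19 are collected and excluded.

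**Allowing for early stopping.** The documents do not give time on treatment in this trial. As an assumption, take it as exponential, S(t) = 0.5^(t / (30.4375 × median in months)), and sum S(t) over the draw days. Ofatumumab uses 9 months, the design PFS median. Duvelisib uses either 15 months (design PFS median) or 7.6 months (Phase 1 median time on treatment at 25 mg or less, Protocol 1.3.2.2).

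| Arm and assumed median | Expected draws, full window | Expected draws through C7D1 |
|---|---|---|
| Ofatumumab, 9 months | 6.7 | 6.7 |
| Duvelisib, 7.6 months | 8.6 | 6.5 |
| Duvelisib, 15 months | 10.7 | 7.2 |

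The share of duvelisib subjects still dosing at C19D1 would be 22% at 7.6 months and 47% at 15 months. These sums leave out draws made within 30 days after an early stop, and unscheduled draws.

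**What the imbalance could do (illustration only).** With the same per-draw probability p of a given grade in both arms and independent draws, the chance of seeing it at least once in k draws is 1 − (1 − p)^k. The values of p are assumptions. The last two columns average over the number of draws under the exponential assumption.

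| p | 8 draws | 14 draws | Ofatumumab, 9 months | Duvelisib, 7.6 to 15 months |
|---|---|---|---|---|
| 1% | 7.7% | 13.1% | 6.5% | 8.2% to 10.1% |
| 5% | 33.7% | 51.2% | 28.5% | 34.1% to 40.9% |
| 10% | 57.0% | 77.1% | 49.0% | 55.3% to 64.1% |

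Clustering within subjects narrows the gap. At a mean p of 3%, independent draws give 21.6% against 34.7% for 8 and 14 draws. A beta-binomial with concentration 10 gives 16.9% against 24.0%, and with concentration 3 it gives 12.2% against 15.7%.

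**Effect of a cut at Cycle 7.** Counting only draws through C7D1, the assumed 5% risk gives 28.5% on ofatumumab and 27.7% to 30.4% on duvelisib (medians 7.6 and 15 months). Most of the artificial gap disappears.

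**The case against.** The rule is the same in both arms and matches the treatment-emergent definition for adverse events. The table is descriptive, with no test attached. Duvelisib draws after Cycle 7 cover time on drug, so what they find is real cumulative risk. Unscheduled draws count, and the protocol calls for extra testing when clinically indicated, so the maximum is not confined to the scheduled visits. Laboratory findings that are clinically significant or lead to a hold are reported as adverse events, and the 24-week Grade 3 or higher adverse event table already gives a common-window comparison for many of them.

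All of this stands, and it rules out stronger readings that a reader might infer:
- That the duvelisib rates are inflated in themselves. They are not. The 30-day cut can only lower the ofatumumab figure, and the problem lies in setting the two crude figures side by side.
- That every duvelisib subject has 14 or more draws. This holds only for those still dosing at C19D1.
- That ofatumumab is never sampled after the last infusion. This applies to subjects who receive all 12 doses. Early stoppers can have a termination-visit draw or, if they stopped for reasons other than progression, a next-cycle Day 1 draw about 28 days later.
- That the bias has a known size. The documents give no per-draw rates.

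The objection does not remove the imbalance in scheduled draws. Nor do the 24-week adverse event tables capture laboratory grades that were never reported as adverse events.

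**Conclusion.** The point holds for the between-arm comparison. The 8 against 14 scheduled draws for subjects who complete planned treatment, and the exclusion of the six later ofatumumab draws, follow directly from Tables 2 and 4 and SAP 7.3.2. The arm-level gap of roughly 2 to 4 expected draws (8.6 − 6.7 = 1.9; 10.7 − 6.7 = 4.0) rests on the exponential assumption and the proxy medians. The percentage differences shown are illustrations under assumed per-draw risks and should not be quoted as estimates of bias. The existing table remains a proper description of on-treatment laboratory toxicity within each arm. It is a weak basis for saying that one arm has more high-grade abnormalities than the other. This is an inexpensive improvement to a descriptive safety summary and does not affect any efficacy conclusion.

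**What to change.** Keep the existing shift table. Add to SAP 7.3.2 a second shift table, from baseline grade to maximum grade within the first 24 weeks after first dose, under the same treatment-emergent rule. State that between-arm statements on laboratory grades will rest on it. Day 168 falls just after the nominal C7D1 draw on day 162, so subjects treated through Cycle 7 have the same 8 scheduled draws in each arm, and the cut agrees with the one SAP 7.3.1 uses for adverse events. If delayed cycles are expected to push C7D1 past day 168, the cut can instead be the nominal C7D1 visit.

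Extending the window to C9D1 would be less suitable. It mixes 56 off-drug days for ofatumumab completers with on-drug duvelisib time, and because visits stop at progression it would not ensure equal draws.

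The cost is one extra table from data already collected. It will not describe late duvelisib laboratory toxicity, which the existing table still shows, and small differences in draw counts from early stopping will remain.

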- **Skin rash:** Subjects who develop Grade 3 or higher skin rashes should have duvelisib held until resolution of symptoms. In the setting of new Grade 1-2 skin rash early intervention is recommended to ameliorate risk of worsening symptoms. Evaluation of concomitant medications, environmental exposure, infections or other contributing factors is recommended.
- **Cardiac:** Subjects who develop Grade 3 or higher cardiac events should have duvelisib held until resolution of symptoms. This includes \geq Grade 3 (≥ 500 ms) QT interval corrected with Fridericia's method (QTcF) prolongation. A \geq Grade 3 QTcF prolongation requires triplicate ECGs with the average measurement used and the use of Fridericia's correction method (QTcF). For subjects with a right or left BBB, a Grade 3 QTc prolongation is defined as an increase in QTcF of >100 ms from the pre-dose ECG to any post dose ECG as the QRS interval is prolonged at Baseline (by approximately 40 ms) in subjects with a BBB

Subjects requiring treatment interruption should be re-evaluated at least weekly until the toxicity improves to \leq Grade 1 or returns to Baseline level. Duvelisib dose will be restarted at doses described in [Table 9](#).

Treatment Interruption for Hematologic Toxicity

Worsening or transient Grade 3 or higher neutropenia, anemia, and/or thrombocytopenia caused by the subject's existing disease (CLL or SLL) or by duvelisib are to be expected. Blood counts should be monitored as prescribed in the protocol with the frequency increased as clinically indicated in the setting of new or worsening Grade 3 or higher cytopenias. Duvelisib dosing may be interrupted at any time, at the discretion of the treating physician.

Treatment with duvelisib should be interrupted for the following symptomatic hematologic toxicities:

- Grade 3 or higher febrile neutropenia
- Grade 3 or higher thrombocytopenia associated with Grade 2 or higher haemorrhage

The subject should be re-evaluated at least weekly until the toxicity improves to \leq Grade 1 or returns to Baseline.

Duvelisib may be withheld up to 42 days for toxicity. Doses withheld for > 42 days due to treatment-related toxicity will result in permanent discontinuation from treatment. Any subject who requires a dose < 5 mg BID due to treatment-related toxicities will be permanently discontinued from treatment. Dose levels are shown in [Table 9](#).

Table 9: Dosing Levels Duvelisib

Dose Level	Dose (mg)
1	25 BID
-1	15 BID
-2	10 BID
-3	5 BID

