8.2.3.2 Immediate Reporting of Medical Events of Interest

Reports or laboratory results of **AST or ALT > 3x ULN in combination with total bilirubin > 2x ULN are medical events of interest**, and therefore immediately reportable events, even if the events do not meet serious adverse event criteria.

Clinical findings of **Grade 3 or higher rash are medical events of interest**, and therefore immediately reportable events, even if the events do not meet serious adverse event criteria. Pre-existing skin conditions that recur would not meet this definition unless the recurrence is of a greater severity/frequency than previously experienced.

All medical events of interest will be reported to the Sponsor or designee within 24 hours of the Investigator's first knowledge of the event, even if the experience does not appear to be related to study drug. Medical Events of Interest should be communicated on the SAE / Medical Events of Interest (MEOI) report form, as described above for SAEs.

Any occupational exposure or exposure of an individual not enrolled in the study to the investigational medicinal product must be reported to the Sponsor or designee within 24 hours of the Investigator's first knowledge of the event, even if the exposure does not result in an adverse event. Unintentional exposures should be communicated on the SAE/MEOI report form, as described above for SAEs.

8.2.3.3 Reporting of Serious Adverse Events to the Institutional Review Board (IRBs)/ Ethics Committee

Verastem or designee shall notify the Investigator and/or the IRBs/ECs per institutional guidelines of potential serious risks from clinical trials or any other sources, including the following:

- Suspected adverse reaction that is both serious and unexpected.
- Any findings from other studies that suggest a significant risk in humans exposed to the drug.
- Any finding from animal or in vitro testing that suggest a significant risk to humans exposed to the drug, such as mutagenicity, teratogenicity, or carcinogenicity; or report of significant organ toxicity at or near the expected human exposure.

Verastem or designee shall notify Central Ethics Committees (CEC) of new serious, related, and unexpected AE(s) or significant risks to subjects, per country requirements.

The Investigator will notify Local Ethics Committees (LECs) of serious, related and unexpected AE(s) or significant risks to subjects, per local country requirements.

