### 3.4 Blinding

This study is open-label and Investigators, site staff, Sponsor and Sponsor designees will have access to treatment assignments for individual subjects. To reduce bias, a blinded independent central review of disease status will be conducted, which will be blinded to individual subject treatment assignments. Investigators, site staff, Sponsor and Sponsor designees will only have access to blinded (pooled) aggregate study data, except for a select number of Sponsor staff, who may review aggregate SAEs and Medical Events of Interest (MEOI) data by treatment groups.

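### The 2-day limit in the combined ALT/AST and bilirubin listing is narrower than the protocol's reportable-event definition and than the sampling schedule, so the listing may not match the reported events

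*SAP*

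**What the plan says.** SAP V4.0 Section 7.3.2 plans a listing of subjects with ALT or AST above 3xULN "with simultaneous total bilirubin" above 2xULN, and then makes concurrency operational: "The elevations of ALT/AST and total bilirubin must occur within 2 days of each other". SAP V1.0 had the same listing without that sentence; it first appears in V2.0.

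Protocol Section 8.2.3.2 uses the same thresholds for expedited reporting: "AST or ALT > 3x ULN in combination with total bilirubin > 2x ULN are medical events of interest". It does not say how close in time the two results must be. Reporting does not depend on the SAP listing: "All medical events of interest will be reported to the Sponsor or designee within 24 hours".

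Section 7.3.2 of the SAP also plans other laboratory outputs. "Listings will be provided for all laboratory test results and for laboratory test results grade 3 and higher", and for tests with CTCAE grades "a shift table from baseline grade to the maximum post-baseline grade will be provided". Only results from the first dose to 30 days after the last dose enter these analyses. The SAP specifies no table or listing of MEOIs. Section 3.4 mentions MEOI data by arm only in connection with selected sponsor staff, "who may review aggregate SAEs and Medical Events of Interest (MEOI) data by treatment groups".

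**The concern.** The same pair of thresholds serves two purposes with two different time rules. Under the protocol, an investigator who sees a transaminase rise followed by a bilirubin rise can reasonably report an MEOI. Under the SAP, the same subject enters the combined listing only if qualifying results fall no more than 2 days apart.

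If planned draws are further apart than 2 days, the rule is in effect a same-draw rule. A sequential case, in which the transaminase has already fallen when the bilirubin rise is first seen, is then missing from the one output built to show the combination. A reader of the study report could find MEOIs that the listing lacks, with nothing in the SAP to reconcile them.

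The signal is relevant to this drug. Protocol Section 1.3.2.2 gives Grade 3 ALT/AST elevation as one of two phase 1 dose-limiting toxicities, and ALT/AST increase as an adverse event in 29% of 55 relapsed/refractory CLL/SLL subjects.

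**Working it through.** The plan states no figure for this listing, so there is none to reproduce. The check compares the 2-day window with the sampling schedule and then with the other planned outputs.

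**1. Gaps between scheduled draws.** The inputs are the blood chemistry row and visit windows of Protocol Table 2 (duvelisib). Table 4 has the same chemistry days for ofatumumab through Cycle 7. The first cycle is 21 days and later cycles are 28 days.

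Minimum gap = nominal gap − late allowance at the first visit − early allowance at the second visit.

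| Interval | Nominal gap (days) | Minimum gap (days) |
|---|---|---|
| C1D1 (predose) to C1D8 | 7 | 7 − 0 − 2 = 5 |
| C1D8 to C2D1 | 14 | 14 − 2 − 2 = 10 |
| C2D1 to C2D15 | 14 | 14 − 2 − 2 = 10 |
| C2D15 to C3D1 | 14 | 14 − 2 − 4 = 8 |
| C3 to C7, each Day 1 to the next | 28 | 28 − 4 − 4 = 20 |
| C7 to C19, each odd-cycle Day 1 to the next | 56 | 56 − 4 − 4 = 48 |

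The shortest gap between two post-dose scheduled draws is 8 days. Tables 2 and 4 also allow samples within 72 hours of the visit. Using that allowance in full at both ends of the shortest interval gives 8 − 3 − 3 = 2 days. This is the only way two scheduled post-dose draws could meet the rule.

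**2. Draws during a hold.** Protocol Section 4.2.1.1 says: "Subjects requiring treatment interruption should be re-evaluated at least weekly". A 7-day retest satisfies the protocol and falls outside the 2-day window. More frequent unscheduled draws are allowed and could fall inside it.

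**3. What the rule captures.** ALT, AST and bilirubin belong to one chemistry panel (Protocol Section 6.3.2). I read the rule as applying to any pair of results above their thresholds.

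- Both above threshold at one draw: listed, even if one rose first.
- Above threshold at separate draws no more than 2 days apart: listed.
- ALT/AST above 3xULN at one draw, bilirubin first above 2xULN at a later draw more than 2 days on, ALT/AST by then at or below 3xULN: not listed.

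**4. Where an unlisted case still appears.** Both values are in the listing of all results. Each analyte contributes its maximum grade to its own shift table. Any adverse event recorded for the case is in the listings of Section 7.3.1. None of these puts the two analytes together.

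**5. Size.** The documents give no rate of combined elevations and no rate of ALT decline, so no count of missed cases can be derived. For illustration only, assume that ALT halves every 4 to 10 days after a hold. The peak that has fallen to exactly 3xULN at a 7-day retest is 3 × 2^(7/half-life): 3 × 2^(7/10) = 4.9xULN for 10 days and 3 × 2^(7/4) = 10.1xULN for 4 days. Lower peaks would no longer overlap with a bilirubin rise first seen at that retest. The conclusion does not use these figures.

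**The case against.** The best defence is that the SAP does what it says. The listing asks for simultaneous elevations, and for analytes on one panel a 2-day tolerance is a sensible definition of that word. The protocol's phrase linking the two thresholds is itself undefined, and Section 7.3.2 does not call its output an MEOI listing. This stands: the two documents differ in scope but do not contradict each other.

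A reader might infer that sequential liver cases vanish from the planned safety outputs. The documents do not support that. The values are listed, MEOIs go to the sponsor within 24 hours, adverse events are listed, and the IDMC reviews all available unblinded safety information (Protocol Section 10.7).

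A reader might also infer a miss rate from an assumed ALT decline. The documents give no such decline. Section 4.2.1.1 calls for a hepatic hold only at Grade 3 or higher, and weekly is the longest permitted retest interval during a hold, not the typical one. Nor is eDISH in the abbreviation list evidence of a dropped output, because ANCOVA and MMRM are also in that list and not used in the V4.0 analyses.

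The phase 1 background needs the same care. The dose-limiting event was at 100 mg BID, whereas this trial starts at 25 mg BID. The 29% pools doses, with 24 of the 55 subjects at 75 mg. It counts adverse events, not values above 3xULN, and says nothing about bilirubin.

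Finally, pairing at any time has a cost. Duvelisib treatment can continue beyond 18 cycles without a fixed end, so unrelated elevations could be joined. Only autoimmune haemolytic anaemia that is uncontrolled or needs more than 20 mg prednisone daily is excluded, so haemolytic bilirubin rises can occur.

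**Conclusion.** The point holds as a mismatch of definitions with a practical consequence. The only SAP output that pairs ALT/AST with bilirubin applies a window that the protocol's event definition lacks and that planned draws almost never meet. A non-overlapping sequential case would be absent from that listing, which therefore may not agree with the MEOIs reported.

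What is lost is the automatic pairing and the link to the MEOIs, not the data. It would go too far to call this the only planned output for hepatic safety or to say that the SAP breaches the protocol. The number of subjects affected is unknown and may be zero. The conclusion rests on the nominal schedule and its windows, and on reading the 2-day rule as applying to any pair of qualifying results. It is a modest point, worth acting on because the change is cheap and the present listing can be recovered from it.

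**What to change.** Amend SAP Section 7.3.2 so that the listing includes every subject with ALT or AST above 3xULN and total bilirubin above 2xULN at any time in the treatment-emergent period. Show the days between the two elevations and the alkaline phosphatase values. Keep the 2-day match as a flag and add a flag for pairs within 30 days. Add a plot of peak ALT/AST against peak bilirubin by arm. State that the list will be reconciled with the reported MEOIs and any difference explained.

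The cost is SAP wording, one changed listing, one figure and the reconciliation. Reviewers will also see some non-specific pairs, such as elevations far apart in time or haemolytic bilirubin rises. The flags and the days-between column let these be set aside. No clinical rule changes.
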